5.2.12 Second Primary Cancer Reporting Requirements
All cases of second primary cancers, including acute myeloid leukemia (AML) and myelodysplastic syndrome (MDS), that occur following treatment on NCI-sponsored trials must be reported to ECOG-ACRIN using Medidata Rave

- **A second malignancy is a cancer that is UNRELATED to any prior anti-cancer treatment (including the treatment on this protocol). Second malignancies require ONLY routine reporting as follows:**
 1. Complete a Second Primary Form in Medidata Rave within 14 days.
 2. Upload a copy of the pathology report to ECOG-ACRIN via Medidata Rave confirming the diagnosis.
 3. If the patient has been diagnosed with AML/MDS, upload a copy of the cytogenetics report (if available) to ECOG-ACRIN via Medidata Rave.
- **A secondary malignancy is a cancer CAUSED BY any prior anti-cancer treatment (including the treatment on this protocol). Secondary malignancies require both routine and expedited reporting as follows:**
 1. Complete a Second Primary Form in Medidata Rave within 14 days.
 2. For this study: Report the diagnosis expeditiously by initially reporting it PROMPTLY upon learning of the secondary malignancy in the Adverse Event Form or Late Adverse Event Form in the appropriate Treatment Cycle or Post Registration folder in Medidata Rave. Once the adverse event is entered into Rave, the Rules Engine on the Expedited Reporting Evaluation Form will confirm whether or not the adverse event requires expedited reporting. The CTEP-AERS report must then be initiated directly from the Expedited Reporting Evaluation Form in Medidata Rave. Do not initiate the CTEP-AERS report via the CTEP-AERS website.
Report under a.) leukemia secondary to oncology chemotherapy, b.) myelodysplastic syndrome, or c.) treatment related secondary malignancy
 3. Upload a copy of the pathology report to ECOG-ACRIN via Medidata Rave and submit a copy to NCI/CTEP confirming the diagnosis.
 4. If the patient has been diagnosed with AML/MDS, upload a copy of the cytogenetics report (if available) to ECOG-ACRIN via Medidata Rave and submit a copy to NCI/CTEP.

NOTE: The ECOG-ACRIN Second Primary Form and the CTEP-AERS report should not be used to report recurrence or development of metastatic disease.

NOTE: If a patient has been enrolled in more than one NCI-sponsored study, the ECOG-ACRIN Second Primary Form must be submitted for the most recent trial. ECOG-ACRIN must be provided with a copy of the form and the associated pathology report and cytogenetics report (if available) even if ECOG-ACRIN was not the patient's most recent trial.

NOTE: Once data regarding survival and remission status are no longer required by the protocol, no follow-up data should be submitted via CTEP-AERS or by the ECOG-ACRIN Second Primary Form.

Rev. Add2

5.3 Comprehensive Adverse Events and Potential Risks list (CAEPR) for Nivolumab (NSC 748726)

The Comprehensive Adverse Events and Potential Risks list (CAEPR) provides a single list of reported and/or potential adverse events (AE) associated with an agent using a uniform presentation of events by body system. In addition to the comprehensive list, a subset, the Specific Protocol Exceptions to Expedited Reporting (SPEER), appears in a separate column and is identified with bold and italicized text. This subset of AEs (SPEER) is a list of events that are protocol specific exceptions to expedited reporting to NCI (except as noted below). Refer to the 'CTEP, NCI Guidelines: Adverse Event Reporting Requirements' http://ctep.cancer.gov/protocolDevelopment/electronic_applications/docs/aeguide_lines.pdf for further clarification. Frequency is provided based on 2069 patients.

Below is the CAEPR for Nivolumab.

NOTE: If an AE meets the reporting requirements of the protocol, and it is listed on the SPEER, it should ONLY be reported expeditiously if the grade being reported exceeds the grade listed in the parentheses next to the event. Since some arms on this protocol use multiple investigational agents, if an AE is listed on multiple SPEERs, use the lower of the grades to determine if expedited reporting is required.

Version 2.4, December 2, 2020¹

Adverse Events with Possible Relationship to Nivolumab (CTCAE 5.0 Term) [n= 2069]			Specific Protocol Exceptions to Expedited Reporting (SPEER)
Likely (>20%)	Less Likely (<=20%)	Rare but Serious (<3%)	
BLOOD AND LYMPHATIC SYSTEM DISORDERS			
	Anemia		Anemia (Gr 3)
CARDIAC DISORDERS			
		Cardiac disorders - Other (cardiomyopathy)	
		Myocarditis	
		Pericardial tamponade ²	
		Pericarditis	
ENDOCRINE DISORDERS			
	Adrenal insufficiency ³		
	Hyperthyroidism ³		
	Hypophysitis ³		
	Hypothyroidism ³		
EYE DISORDERS			
		Blurred vision	
		Dry eye	
		Eye disorders - Other (diplopia) ³	
		Eye disorders - Other (Graves ophthalmopathy) ³	
		Eye disorders - Other (optic neuritis retrobulbar) ³	
		Eye disorders - Other (Vogt-Koyanagi-Harada)	
	Uveitis		

Adverse Events with Possible Relationship to Nivolumab (CTCAE 5.0 Term) [n= 2069]			Specific Protocol Exceptions to Expedited Reporting (SPEER)
Likely (>20%)	Less Likely (<=20%)	Rare but Serious (<3%)	
GASTROINTESTINAL DISORDERS			
	Abdominal pain		Abdominal pain (Gr 2)
	Colitis ³		
		Colonic perforation ³	
	Diarrhea		Diarrhea (Gr 3)
	Dry mouth		Dry mouth (Gr 2)
		Enterocolitis	
		Gastritis	
		Mucositis oral	
	Nausea		Nausea (Gr 2)
	Pancreatitis ⁴		
GENERAL DISORDERS AND ADMINISTRATION SITE CONDITIONS			
Fatigue			Fatigue (Gr 3)
	Fever		Fever (Gr 2)
	Injection site reaction		Injection site reaction (Gr 2)
HEPATOBILIARY DISORDERS			
		Hepatobiliary disorders - Other (immune-mediated hepatitis)	
IMMUNE SYSTEM DISORDERS			
		Allergic reaction ³	
		Autoimmune disorder ³	
		Cytokine release syndrome ⁵	
		Immune system disorders - Other (GVHD in the setting of allograft transplant) ^{3,6}	
		Immune system disorders - Other (sarcoidosis) ³	
INJURY, POISONING AND PROCEDURAL COMPLICATIONS			
	Infusion related reaction ⁷		
INVESTIGATIONS			
	Alanine aminotransferase increased ³		Alanine aminotransferase increased³ (Gr 3)
	Aspartate aminotransferase increased ³		Aspartate aminotransferase increased³ (Gr 3)
	Blood bilirubin increased ³		Blood bilirubin increased³ (Gr 2)
	CD4 lymphocytes decreased		CD4 lymphocyte decreased (Gr 4)
	Creatinine increased		
	Lipase increased		
	Lymphocyte count decreased		Lymphocyte count decreased (Gr 4)
	Neutrophil count decreased		
	Platelet count decreased		
	Serum amylase increased		
METABOLISM AND NUTRITION DISORDERS			
	Anorexia		

Adverse Events with Possible Relationship to Nivolumab (CTCAE 5.0 Term) [n= 2069]			Specific Protocol Exceptions to Expedited Reporting (SPEER)
Likely (>20%)	Less Likely (<=20%)	Rare but Serious (<3%)	
		Hyperglycemia	Hyperglycemia (Gr 2)
		Metabolism and nutrition disorders - Other (diabetes mellitus with ketoacidosis) ³	
MUSCULOSKELETAL AND CONNECTIVE TISSUE DISORDERS			
	Arthralgia		
		Musculoskeletal and connective tissue disorder - Other (polymyositis)	
		Myositis	
		Rhabdomyolysis	
NERVOUS SYSTEM DISORDERS			
		Encephalopathy ³	
		Facial nerve disorder ³	
		Guillain-Barre syndrome ³	
		Myasthenia gravis ³	
		Nervous system disorders - Other (demyelination myasthenic syndrome)	
		Nervous system disorders - Other (encephalitis) ³	
		Nervous system disorders - Other (meningoencephalitis)	
		Nervous system disorders - Other (meningoradiculitis) ³	
		Nervous system disorders - Other (myasthenic syndrome)	
		Peripheral motor neuropathy	
		Peripheral sensory neuropathy	
		Reversible posterior leukoencephalopathy syndrome ³	
RENAL AND URINARY DISORDERS			
		Acute kidney injury ³	
		Renal and urinary disorders - Other (immune-mediated nephritis)	
RESPIRATORY, THORACIC AND MEDIASTINAL DISORDERS			
	Pleural effusion ³		
	Pneumonitis ³		
		Respiratory, thoracic and mediastinal disorders - Other (bronchiolitis obliterans with organizing pneumonia) ³	
SKIN AND SUBCUTANEOUS TISSUE DISORDERS			
		Erythema multiforme ³	
	Pruritus ³		Pruritus³ (Gr 2)
	Rash maculo-papular ³		Rash maculo-papular³ (Gr 2)

Adverse Events with Possible Relationship to Nivolumab (CTCAE 5.0 Term) [n= 2069]			Specific Protocol Exceptions to Expedited Reporting (SPEER)
Likely (>20%)	Less Likely (<=20%)	Rare but Serious (<3%)	
		Skin and subcutaneous tissue disorders - Other (bullous pemphigoid)	
	Skin and subcutaneous tissue disorders - Other (Sweet's Syndrome) ³		
	Skin hypopigmentation ³		
		Stevens-Johnson syndrome	
		Toxic epidermal necrolysis	

¹This table will be updated as the toxicity profile of the agent is revised. Updates will be distributed to all Principal Investigators at the time of revision. The current version can be obtained by contacting [contact]. Your name, the name of the investigator, the protocol and the agent should be included in the e-mail.

²Pericardial tamponade may be related to possible inflammatory reaction at tumor site.

³Nivolumab being a member of class of agents involved in the inhibition of "immune checkpoints", may result in severe and possibly fatal immune-mediated adverse events probably due to T-cell activation and proliferation. This may result in autoimmune disorders that can include (but are not limited to) autoimmune hemolytic anemia, acquired anti-factor VIII immune response, autoimmune aseptic meningitis, autoimmune hepatitis, autoimmune nephritis, autoimmune neuropathy, autoimmune thyroiditis, bullous pemphigoid, exacerbation of Churg-Strauss Syndrome, drug rash with eosinophilia systemic symptoms [DRESS] syndrome, facial nerve disorder (facial nerve paralysis), limbic encephalitis, hepatic failure, pure red cell aplasia, pancreatitis, ulcerative and hemorrhagic colitis, endocrine disorders (e.g., autoimmune thyroiditis, hyperthyroidism, hypothyroidism, autoimmune hypophysitis/hypopituitarism, thyrotoxicosis, and adrenal insufficiency), sarcoid granuloma, myasthenia gravis, polymyositis, and Guillain-Barre syndrome.

⁴Pancreatitis may result in increased serum amylase and/or more frequently lipase.

⁵Cytokine release syndrome may manifest as hemophagocytic lymphohistiocytosis with accompanying fever and pancytopenia.

⁶Complications including hyperacute graft-versus-host disease (GVHD), some fatal, have occurred in patients receiving allo stem cell transplant (SCT) after receiving Nivolumab. These complications may occur despite intervening therapy between receiving Nivolumab and allo-SCT.

⁷Infusion reactions, including high-grade hypersensitivity reactions which have been observed following administration of nivolumab, may manifest as fever, chills, shakes, itching, rash, hypertension or hypotension, or difficulty breathing during and immediately after administration of nivolumab.

Adverse events reported on Nivolumab trials, but for which there is insufficient evidence to suggest that there was a reasonable possibility that Nivolumab caused the adverse event:

BLOOD AND LYMPHATIC SYSTEM DISORDERS - Leukocytosis

CARDIAC DISORDERS - Atrial fibrillation; Atrioventricular block complete; Heart failure; Ventricular arrhythmia

EAR AND LABYRINTH DISORDERS - Vestibular disorder

EYE DISORDERS - Eye disorders - Other (iritocyclitis); Optic nerve disorder; Periorbital edema

GASTROINTESTINAL DISORDERS - Constipation; Duodenal ulcer; Flatulence; Gastrointestinal disorders - Other (mouth sores); Vomiting

GENERAL DISORDERS AND ADMINISTRATION SITE CONDITIONS - Chills; Edema limbs; Malaise; Pain

HEPATOBILIARY DISORDERS - Bile duct stenosis

IMMUNE SYSTEM DISORDERS - Anaphylaxis; Immune system disorders - Other (autoimmune thrombotic microangiopathy); Immune system disorders - Other (limbic encephalitis)

INFECTIONS AND INFESTATIONS - Bronchial infection; Lung infection; Sepsis; Upper respiratory infection

INVESTIGATIONS - Blood lactate dehydrogenase increased; GGT increased; Investigations - Other (protein total decreased); Lymphocyte count increased; Weight loss

METABOLISM AND NUTRITION DISORDERS - Dehydration; Hyperuricemia; Hypoalbuminemia; Hypocalcemia; Hyponatremia; Hypophosphatemia

MUSCULOSKELETAL AND CONNECTIVE TISSUE DISORDERS - Back pain; Musculoskeletal and connective tissue disorder - Other (musculoskeletal pain); Musculoskeletal and connective tissue disorder - Other (polymyalgia rheumatica); Myalgia; Pain in extremity

NEOPLASMS BENIGN, MALIGNANT AND UNSPECIFIED (INCL CYSTS AND POLYPS) - Neoplasms benign, malignant and unspecified (incl cysts and polyps) - Other (Histiocytic necrotizing lymphadenitis)

NERVOUS SYSTEM DISORDERS - Dizziness; Headache; Intracranial hemorrhage

PSYCHIATRIC DISORDERS - Insomnia

RENAL AND URINARY DISORDERS - Hematuria; Renal and urinary disorders - Other (tubulointerstitial nephritis)

RESPIRATORY, THORACIC AND MEDIASTINAL DISORDERS - Bronchospasm; Cough; Dyspnea; Hypoxia

SKIN AND SUBCUTANEOUS TISSUE DISORDERS - Alopecia; Dry skin; Hyperhidrosis; Pain of skin; Photosensitivity; Rash acneiform; Skin and subcutaneous tissue disorders - Other (rosacea)

VASCULAR DISORDERS - Flushing; Hypertension; Hypotension; Vasculitis

NOTE: Nivolumab in combination with other agents could cause an exacerbation of any adverse event currently known to be caused by the other agent, or the combination may result in events never previously associated with either agent.

Rev. Add1
Rev. Add3

5.4 Dose Modifications

Dose modifications for platinum and etoposide are permitted for toxicity according to the prescribing information. Dose modification guidelines are provided below.

In order to ensure accurate determination of the duration of adverse events, patients must be evaluated at least once weekly (intervals should not be longer than every 7 days) while awaiting resolution of any adverse event whose duration may necessitate dose modification.

5.4.1 Cisplatin/Carboplatin and Etoposide Supportive Care

NOTE: Dose reductions for all events are permanent and should be for all subsequent cycles. Patients may receive a maximum of two chemotherapy dose reductions. If a third chemotherapy dose reduction is required, the patient should discontinue chemotherapy protocol treatment. If different percentages of dose reductions for a specific drug are required because of two different types of toxicities, the greater percentage dose reduction should be undertaken.

Rev. Add3

5.4.1.1 Hematologic Toxicity

Neutropenia and/or Thrombocytopenia

Granulocyte or platelet counts for Day 1: Based on counts within 3 days of the start of each cycle, give the following:

Granulocytes/mm ³		Platelets / mm ³	Cisplatin/carboplatin and etoposide
ANC ≥ 1,500	and	PLT ≥ 100,000	100%
ANC < 1,500	and/or	PLT < 100,000	Hold dose*

* Hold cisplatin/carboplatin and etoposide; repeat counts at least once weekly and reinstitute therapy at 100% when granulocytes ≥ 1,500/mm³ and platelets ≥ 100,000/mm³ if recovery within 7 days.

If cisplatin administered, reinstitute at 75% of the original dose if more than 7 days. If carboplatin administered, reinstitute carboplatin AUC with decrease by one dose level (i.e. starting dose of AUC 6 dose reduction 1= AUC 5), if more than 7 days.

If counts do not reach these levels within 3 weeks of the next scheduled treatment, discontinue chemotherapy protocol therapy.

Neutropenia or Febrile Neutropenia

For nadir neutropenia in the absence of fever or with fever that is successfully treated by oral antibiotics, there will be no dose adjustment. Filgrastim, sargramostim, or pegfilgrastim are allowed (for the next cycle of chemotherapy). Growth factors may be used in

accordance with American Society of Clinical Oncology (ASCO) and NCCN guidelines.

For treatment delays (hold both chemotherapy and nivolumab) due to chemotherapy toxicities of more than 7 days, both chemotherapy drugs, cisplatin and etoposide, should be dose reduced by 25%. If carboplatin administered, reinstitute carboplatin AUC with decrease by one dose level (i.e. starting dose of AUC 6 dose reduction 1= AUC 5), if more than 7 days.

Rev. Add4

For neutropenic fever (ANC <1000/mm³ with a single temperature of >38.3 degrees C (101 degrees F) or a sustained temperature of ≥ 38 degrees C (100.4 degrees F) for more than one hour) requiring intravenous antibiotics, the doses of all chemotherapy drugs should be reduced by 25% for the next cycle. If carboplatin administered, reinstitute carboplatin AUC with decrease by one dose level (i.e. starting dose of AUC 6 dose reduction 1= AUC 5), if more than 7 days. If counts do not recover within 3 weeks, discontinue chemotherapy protocol therapy.

Thrombocytopenia

For grade 4 nadir platelet count decrease (platelets < 25,000 mm³), the dose of all chemotherapy drugs should be reduced by 25% from the previous dose for the next cycle. If carboplatin administered, reinstitute carboplatin AUC with decrease by one dose level (i.e. starting dose of AUC 6 dose reduction 1= AUC 5), if more than 7 days. If counts do not recover within 3 weeks, discontinue chemotherapy protocol therapy.

Anemia

No dose reductions will be made for anemia. Patients should be supported per the treating physician's discretion. The use of blood transfusions for anemia will be allowed as indicated. The use of growth factors for anemia is not permitted during cycle 1 for patients and may be used for cycle 2 (please refer to supportive care guidelines in Section [5.5](#)).

5.4.1.2

Gastrointestinal Toxicity, Nausea and Vomiting

All patients should receive antiemetics* to prevent nausea and vomiting. Specific antiemetic therapy is left to the discretion of the treating physician (steroids and 5-HT3 antagonists should be used). If vomiting is severe, consider hospital admission and/or use of aprepitant if possible. Do not modify chemotherapy doses, until antiemetics have been maximally optimized.

*Aprepitant, when given once daily for 14 days as a 100 mg capsule with an oral contraceptive containing 35 mcg

of ethinyl estradiol and 1 mg of norethindrone, decreased the AUC of ethinyl estradiol by 43% and decreased the AUC of norethindrone by 8%. Women of childbearing potential using pregnancy contraception that includes ethinyl estradiol should not receive Aprepitant for the treatment of nausea/delayed emesis. Patients may change to a different method of contraception if they wish to use Aprepitant.

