5.4.1.9 Grade 3 or 4 Non-Hematologic Toxicity

If patient develops grade 3 or 4 non-hematologic toxicity attributed to protocol therapy but not detailed above [excluding the following: anorexia, fatigue and fever without grade 3 or 4 neutrophil count decrease (neutropenia)] hold all therapy. Therapy can be restarted if the toxicity has resolved to < grade 1 by the time of the next treatment. Doses of all chemotherapy should then be reduced by 25% (of the dose received during the previous cycle). If carboplatin administered, reinstitute carboplatin AUC with decrease by one dose level (i.e. starting dose of AUC 6 dose reduction 1= AUC 5). If chemotherapy is held for more than 3 weeks, remove the patient from all protocol therapy.

A clinically relevant overlap in toxicity may arise between the immune-related dermatologic and cardiac toxicities attributed to nivolumab and dermatologic and cardiac toxicities attributed to etoposide. The management of overlapping toxicities should be guided by clinical judgment and an assessment of the most likely causative etiology, with special consideration given to the potential

for immune-mediated toxicities. Nivolumab administration should be delayed for toxicities as indicated in the management algorithms ([Appendix III](#)) that in the opinion of the treating physician are related to nivolumab. Please refer to Section [5.4.2.2](#).

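### After neutropenic fever or a grade 4 platelet nadir, Section 5.4.1.1 gives two conflicting carboplatin instructions for one event; state a single rule without the 7-day condition

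*Combined protocol and SAP*

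**What the plan says.** Section 5.1 lets the treating physician choose cisplatin or carboplatin, and start carboplatin at AUC 5 or 6, for at most 4 chemotherapy cycles. Section 5.4.1.1 then sets the hematologic dose rules.

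- **Neutropenic fever needing intravenous antibiotics.** The general instruction is that "the doses of all chemotherapy drugs should be reduced by 25% for the next cycle". The carboplatin sentence that follows asks for a "decrease by one dose level (i.e. starting dose of AUC 6 dose reduction 1= AUC 5), if more than 7 days".
- **Grade 4 nadir platelets.** The general instruction is that "the dose of all chemotherapy drugs should be reduced by 25% from the previous dose for the next cycle". The same carboplatin sentence follows, with the same 7-day condition.
- **Recovery limit.** Both paragraphs end with "If counts do not recover within 3 weeks, discontinue chemotherapy protocol therapy".

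Three other rules use related wording:

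- **Day 1 counts (5.4.1.1).** Hold, then "repeat counts at least once weekly and reinstitute therapy at 100% when granulocytes" and platelets recover within 7 days. Otherwise, "If cisplatin administered, reinstitute at 75% of the original dose if more than 7 days", and carboplatin restarts one level down.
- **Treatment delays of more than 7 days (5.4.1.1).** Here "both chemotherapy drugs, cisplatin and etoposide, should be dose reduced by 25"%, and carboplatin is handled separately by AUC level.
- **Grade 3 or 4 non-hematologic toxicity (5.4.1.9).** A 25% cut of all chemotherapy is followed by a carboplatin "decrease by one dose level (i.e. starting dose of AUC 6 dose reduction 1= AUC 5). If chemotherapy is held" for more than 3 weeks, the patient leaves protocol therapy. There is no 7-day condition on the level drop.

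Section 5.4.1 makes reductions permanent, allows at most two, and takes the greater percentage when two different types of toxicity call for different cuts.

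**The concern.** Carboplatin is one of the chemotherapy drugs, so in the fever and platelet paragraphs it falls under both sentences. One sentence cuts it by a quarter at once. The other cuts it by one AUC level, and only after 7 days. Nothing says whether the second sentence replaces the first, adds to it, or was meant to be the only carboplatin rule.

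The 7-day condition makes sense in the Day 1 rule, where early recovery restarts at full dose and late recovery restarts lower. Placed after an unconditional 25% cut, it no longer has a clear meaning.

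These are serious toxicities. Two sites could give different doses after the same event, and the choice is permanent: an event in cycle 1 fixes the dose for up to 3 of the 4 cycles. On one reading, the patient whose marrow recovers more slowly gets the higher dose.

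**Working it through.** The protocol states no figure for the resulting dose, so there is nothing to reproduce. The check applies each reading to the permitted starting doses.

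**Inputs.** Starting dose AUC 5 or 6 (5.1). General cut 25% and one-level drop AUC 6 to AUC 5 (5.4.1.1). Calvert formula: dose in mg = AUC × (CrCl + 25), with a creatinine clearance of at least 50 mL/min and a cap of 125 mL/min (8.3.5). I take the 7 days as time to count recovery. That is an inference: both paragraphs speak of reinstituting carboplatin and set a 3-week recovery limit, but neither defines the 7 days.

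**Target AUC from a start of AUC 6**

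| Reading for carboplatin | 7 days or less | More than 7 days |
|---|---|---|
| A. 25% cut, replaced by the level drop after 7 days | 6 × 0.75 = 4.5 (25% cut) | 5 (1 − 5/6 = 16.7% cut) |
| B. 25% cut, with the level drop added after 7 days | 4.5 (25% cut) | level first: 5 × 0.75 = 3.75 (37.5% cut); 25% first: 4.5 − 1 = 3.5 (41.7% cut) |
| C. Carboplatin sentence alone governs carboplatin | 6 (no cut) | 5 (16.7% cut) |

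Under B the order is not stated, and the 3.5 also assumes that a level is 1 AUC unit, as in the protocol's only example.

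**In milligrams.** The Calvert factor is 50 + 25 = 75 at CrCl 50 and 125 + 25 = 150 at the cap.

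- Reading A, slow minus quick recovery: (5 − 4.5) × 75 = 37.5 mg, to 0.5 × 150 = 75 mg more carboplatin for the slower patient.
- After more than 7 days, highest minus lowest reading: (5 − 3.5) × 75 = 112.5 mg, to 1.5 × 150 = 225 mg. With the level-first order, the gap is 1.25 × 75 = 93.75 mg to 1.25 × 150 = 187.5 mg.
- After 7 days or less, C against A or B: (6 − 4.5) × 75 = 112.5 mg, to 225 mg.

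**From a start of AUC 5.** A 25% cut gives 5 × 0.75 = 3.75. A one-level drop cannot be computed, because no level below AUC 5 is stated. If a level is 1 unit (assumption), it gives AUC 4 (20% cut); if half a unit, AUC 4.5 (10% cut).

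**Does other text settle it?**

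- The greater-percentage rule in 5.4.1 is for two different types of toxicity, not two instructions for one event.
- Section 5.4 permits modification according to the prescribing information and calls the text guidelines. It does not rank the two sentences.
- The delay rule points to a split: a percentage for cisplatin and etoposide, a level for carboplatin.
- Section 5.4.1.9 shows the level drop without the 7-day condition. It too follows a 25% cut of all chemotherapy, so it supports removing the condition but does not itself say which cut governs.

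**The case against.** The strongest objection concerns the inversion. A reader might infer that the protocol directs a higher carboplatin dose for patients who recover slowly. The documents do not support that. It needs reading A, in which the 25% sentence covers carboplatin at first and is then displaced after 7 days. Under B the slow patient gets less than the quick one. Under C the slow patient is cut and the quick one is not. A site that extended the greater-percentage rule to a single event would give AUC 4.5 in both cases. Recovery speed is also an inference about what the 7 days measure. This all stands, so the inversion is one possible result and not the finding itself.

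Reading C deserves weight, because the Day 1 and delay rules both give cisplatin a percentage and carboplatin a level. But the fever and platelet paragraphs say all chemotherapy drugs, and C would leave carboplatin at full dose after a serious toxicity with quick recovery. It moves the problem without removing it.

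The practical reach is limited. After febrile neutropenia, Section 5.5 mandates growth factor use or dose reduction, which softens the conflict there; it offers no such alternative for grade 4 thrombocytopenia. The 0.5 AUC gap in reading A is half the 1-unit difference already left to discretion at the start. The documents give no frequency for these events.

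A reader might also infer a threat to the PFS comparison. The chemotherapy rule is the same in both arms, and nothing in the documents ties it to alpha, power or sample size.

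**Conclusion.** The concern holds as a conflict between two instructions for one event, not as missing detail. Depending on the reading, a patient starting at AUC 6 receives AUC 4.5 or 6 after quick recovery, and anywhere from 3.5 to 5 after slow recovery. Each of those spans is worth 112.5 to 225 mg per dose over the protocol's creatinine clearance range. The inversion (25% cut against 16.7%) arises only if the level drop replaces the 25% cut.

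The conclusion rests on carboplatin counting as a chemotherapy drug, which is plain. The slow and quick labels rest on the 7 days meaning count recovery, which is probable but unstated. The 3.5 rests on a 1-unit level.

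The scope is carboplatin-treated patients with one of these two events, within at most 4 cycles. The effect is on dosing safety and consistency between sites. It should be corrected, but it does not touch the statistical design.

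**What to change.** In the neutropenic fever and grade 4 platelet paragraphs, delete the 7-day condition from the carboplatin sentence and state one unconditional rule. Deleting the condition alone is not enough, because the 25% cut of all drugs would still sit beside the level drop.

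The form closest to the delay rule and to 5.4.1.9 is: *reduce cisplatin and etoposide by 25%; for carboplatin, reduce by one AUC level instead of the 25%.* The clinical team should confirm this, because from AUC 6 it is a smaller cut (16.7%) than the literal 25%: AUC 5 where readings A and B give 4.5 after quick recovery. If they want the full 25% for carboplatin, delete the carboplatin sentence from these two paragraphs instead.

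Also state the carboplatin level or levels below AUC 5, with the step size set by the clinical team. AUC 5 is a permitted start and two reductions are allowed, yet only the step from 6 to 5 is given.

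The cost is two short wording changes and one added line, with no effect on alpha, power or sample size.
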